8.3.7 REPORTING EVENTS TO PARTICIPANTS

N/A

8.3.8 EVENTS OF SPECIAL INTEREST

N/A

8.3.9 REPORTING OF PREGNANCY

Female participants must confirm that they are not pregnant or breastfeeding and if they become pregnant during the course of the study, participants must notify the study investigator immediately. A pregnancy test is obtained at study enrollment and at each visit to help assure that the participant is not pregnant. If a participant is found to be pregnant, study medication will be stopped indefinitely, and the coded medication will be unmasked. The participant, PCP, and investigator will be notified of the assigned treatment and the associated risks.

8.4 UNANTICIPATED PROBLEMS

8.4.1 DEFINITION OF UNANTICIPATED PROBLEMS (UP)

The Office for Human Research Protections (OHRP) considers unanticipated problems involving risks to participants or others to include, in general, any incident, experience, or outcome that meets all of the following criteria:

- Unexpected in terms of nature, severity, or frequency given (a) the research procedures that are described in the IRB-approved research protocol and informed consent document; and (b) the characteristics of the participant population being studied;
- Related or possibly related to participation in the research (“possibly related” means there is a reasonable possibility that the incident, experience, or outcome may have been caused by the procedures involved in the research); and
- Suggests that the research places participants or others at a greater risk of harm (including physical, psychological, economic, or social harm) than was previously known or recognized.

8.4.2 UNANTICIPATED PROBLEM REPORTING

The investigator will report unanticipated problems (UPs) to the reviewing IRB and to the SDRC/principal investigator (PI). The UP report will include the following information:

- Protocol identifying information: protocol title and number, PI's name, and the IRB project number;
- A detailed description of the event, incident, experience, or outcome;
- An explanation of the basis for determining that the event, incident, experience, or outcome represents an UP;
- A description of any changes to the protocol or other corrective actions that have been taken or are proposed in response to the UP.

To satisfy the requirement for prompt reporting, UPs will be reported using the following timeline:

- UPs that are serious adverse events (SAEs) must be reported to the IRB and to the SDRC/study sponsor within one working day from the date the investigator was aware of the event.
- All other UP will be reported to the IRB and to the DCC/study sponsor within 10 days of the investigator becoming aware of the problem.
- All UPs should be reported to appropriate institutional officials (as required by an institution's written reporting procedures), the supporting agency head (or designee), and the Office for Human Research Protections within 10 days of the IRB's receipt of the report of the problem from the investigator.
- Reports should be sent to: [contact]
- All timelines related to SAE reporting with details are provided in protocol section 8.3.6.

8.4.3 REPORTING UNANTICIPATED PROBLEMS TO PARTICIPANTS

These would be reported to participants if they are unexpected, related or possibly related, and suggest a greater risk of harm to participants.

9 STATISTICAL CONSIDERATIONS

9.1 STATISTICAL HYPOTHESES

- Primary Efficacy Hypothesis: Buspirone at 10 mg three times daily for 4 weeks is better than placebo in improving early satiety and postprandial fullness in adults with symptoms of gastroparesis measured as change in the PAGI-SYM postprandial fullness/early satiety subscore.
- Secondary Efficacy Hypotheses: Buspirone at 10 mg three times daily for 4 weeks is better than placebo in improving the following outcomes:
 1. Changes in GCSI total score
 2. Changes in PAGI-SYM subscores: nausea/vomiting, bloating, upper abdominal pain, GERD
 3. Changes in PAGI-SYM severity scores: Nausea, stomach fullness, inability to finish a normal-sized meal, feeling excessively full after meals, loss of appetite, bloating, upper abdominal pain
 4. Changes in Gastrointestinal Symptom Rating Scale (GSRS) total score
 5. Changes in Clinical Patient Grading Assessment Scale (CPGAS) score
 6. Changes in PAGI-QOL total score
 7. Changes in the Hospital Anxiety and Depression Scale (HADS) total scores for anxiety and depression

8. Changes in Patient Health Questionnaire (PHQ-15) total somatization score
9. Changes in the SF-36v2 Quality of Life questionnaire physical and mental components scores
10. Changes in percent of gastric emptying retention

9.2 SAMPLE SIZE DETERMINATION

Summary of sample size and computation of primary outcome:

The primary outcome variable is change in the PAGI-SYM postprandial fullness/early satiety subscore from baseline to 4 weeks. This subscore is calculated by averaging the scores for 4 PAGI-SYM items: stomach fullness, inability to finish a normal-sized meal, feeling excessively full after meals, and loss of appetite. Each item score ranges from 0 (none) to 5 (very severe) on an ordinal scale. The 4-item average is treated as continuous in the primary ANCOVA analysis of change and for sample size purposes.

The planned 108 participants sample size for this trial was derived using the following assumptions and methods:

- 2 equal size groups
- Power=90%
- Type 1 error (2-sided) = 0.05
- Two-sided tests
- Sample size increased by 10% to allow for 10% loss in primary outcome measure
- Placebo group assumptions: Based on the APRON RCT placebo data [9], we assumed that:
 - Mean (SD) change in postprandial fullness/early satiety subscore at 4-weeks = 3.7 (0.8)
 - Change from baseline at 4-weeks of fullness/early satiety subscore = -0.7 (1.0)
 - Correlation of postprandial fullness/early satiety subscore at baseline and 4-weeks = 0.55
- Method of analysis = ANCOVA of the change in the primary outcome score controlling for baseline value of the primary outcome score
- Intention-to-Treat Analysis using all randomized participants, corrected for missing outcome data:
 - Multiple imputation of the ANCOVA model using the chained equations method with 50 imputations using the Stata Software Command: *mi*
- Minimal Clinical Important Difference (MCID) = 0.62 SD (0.5 subscore points)
- Sample size software: Stata Software Command: *power repeated*
- **Sample size = 108 total (54 per group)**

Sample size for the primary outcome varying the MCID

MCID in SD units	0.3 SD	0.50 SD	0.62 SD*	1 SD
MCID subscore units	0.24	0.4	0.5	0.8
Total sample size	460	168	108	42
Number per group	230	84	54	21

* MCID between investigator-related severity and fullness/early satiety subscore range=0.62-0.70 SD [25]

For the key secondary outcome, symptom improvement by 1-point or more in the PAGI-SYM GSCI total score from baseline to week 4, we determined that the total sample size of 108 participants (54 per group) gives 80% power to detect an MCID for a relative improvement ratio=1.8 (60% buspirone vs. 32% placebo based on APRON

placebo data)). We used a nominal Type 1 error of 5%, with no corrections of the Type 1 error for the multiplicity of secondary outcomes.

The investigators conducting this trial have previously recruited for two trials for the GpCRC and along with their experiences in their clinic research were confident that the estimated number of 18 participants per site at a rate of one participant per month per site was a recruitment target that could be met.

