4.2 SCIENTIFIC RATIONALE FOR STUDY DESIGN

The study design is a multi-center, randomized, double-masked, placebo-controlled, parallel treatment groups phase 2 trial.

Rationale for a Placebo Group: Currently, there are few effective treatments for symptoms in participants with gastroparesis and related syndromes. Studies of various agents have shown placebo effects ranging from 10% and

higher. In the NIDDK GpCRC Aprepitant for the Relief of Nausea (APRON) trial, 40% of the participants treated with placebo improved on the primary outcome [9]. In the NIDDK GpCRC 48-week Outcomes paper, approximately 28% of the participants showed substantial symptomatic improvement at 48 weeks with Standard of Care (SOC) [23]. Therefore, it is important to have a placebo group to be able to discriminate a treatment effect over and above SOC and the lifestyle advice provided to all of these participants.

In addition, in order to assess the efficacy of an agent in gastroparesis, a placebo group is needed to determine the relative efficacy in improving symptoms and physical functions. In order to have the highest quality of evidence to test our hypothesis, the BESST trial uses a randomized, double-masked, placebo-controlled study design.

The trial is double-masked to prevent bias by investigators and participants. The trial is 4 weeks since the Minimum Clinically Important Difference (MCID) in gastroparesis symptoms has been shown in the literature to be detected in that timeframe. The trial is powered at 90% to detect a MCID in the PAGI-SYM questionnaire postprandial fullness/early satiety subscore primary outcome measure; it is powered at 80% to detect a MCID in the GCSI total score, the key secondary outcome.

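### The planning inputs in section 9.2 conflict, and for the planned ANCOVA they give about 69% or 95% power, not the stated 90%

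*Combined protocol and SAP*

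**What the plan says.** Section 9.2 (Sample Size Determination) takes its placebo assumptions from an earlier trial of the same consortium. Three of them matter here. One line, worded as a change, reads "Mean (SD) change in postprandial fullness/early satiety subscore at 4-weeks = 3.7 (0.8". A separate line gives a second and different figure for what is nominally the same quantity: "Change from baseline at 4-weeks of fullness/early satiety subscore = -0.7 (1.0". The third assumption is that the subscores at the two visits correlate at 0.55.

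The target difference is given as "Minimal Clinical Important Difference (MCID) = 0.62 SD (0.5 subscore points", so the scaling SD is 0.5/0.62 = 0.81. The named analysis is an ANCOVA of the change with the baseline subscore as covariate, at two-sided 0.05 and 90% power. Attrition is handled by "Sample size increased by 10% to allow for 10% loss in primary outcome measure". The result is 108 participants, 54 per group, with a table for four effect sizes. Section 4.2 (Scientific Rationale for Study Design) repeats the power as a property of the trial: "The trial is powered at 90% to detect a MCID in the PAGI-SYM questionnaire postprandial fullness/early satiety subscore primary outcome measure".

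**The concern.** Two adjacent lines both call their figure the 4-week change, with different means and different SDs. On a 0 to 5 scale where higher is worse, a mean of 3.7 next to a change of -0.7 can only be a score level. It is either the baseline level (week-4 mean 3.0) or the week-4 level (baseline mean 4.4). The first is the more natural reading, but the text does not decide it.

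The choice matters because ANCOVA power depends on the week-4 SD and the correlation. Only one score SD is listed, and it does not go with the listed change SD unless the other visit has a quite different spread. A reader who follows the listed inputs and the named method does not arrive at 90%. If power is really near 69%, a null result would be reported as coming from a trial with 90% power.

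**Working it through.** **Inputs (section 9.2).** Score SD 0.8; correlation r = 0.55; change SD 1.0; difference 0.5; two-sided alpha 0.05; power 90%; 54 per group; 10% loss, which leaves 54 × 0.9 = 48.6 per group.

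**1. Do the SDs agree?** With 0.8 at both visits, the change SD is 0.8 × √(2 × (1 − 0.55)) = 0.759. Letting the SD run over 0.75–0.85 and r over 0.545–0.555 gives 0.71–0.81. The listed 1.0 is at least 0.95 before rounding, so rounding does not close the gap. To keep 0.8, 0.55 and 1.0 together, the other visit's SD s must satisfy s² − 2 × 0.55 × 0.8 × s + 0.64 = 1, so s = 1.184.

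**2. Reproducing the plan's 54 per group.** n = 2 × (1.96 + 1.2816)² × SD²/d²:

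| Basis | SD | d = 0.24 | 0.4 | 0.5 | 0.8 |
|---|---|---|---|---|---|
| Plan's table | – | 230 | 84 | 54 | 21 |
| Change score, implied SD, rounded up, × 1.1 | 0.759 | 232.1 | 83.6 | 53.9 | 20.9 |
| Raw score, no inflation | 0.8 | 233.5 | 84.1 | 53.8 | 21.0 |

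Both routes come close to the table. The second contradicts the stated 10% increase, so the first is the likelier origin. That is an inference, because 0.759 appears nowhere in the plan. Two other routes miss 54 at d = 0.5:

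- Listed change SD of 1.0: 84.06, so 85 per group, and 94 after × 1.1.
- ANCOVA with 0.8 at both visits, residual SD 0.8 × √(1 − 0.55²) = 0.668: 37.5, so 38 per group, and 42 after × 1.1.

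**3. Power of the planned ANCOVA.** Residual SD = week-4 SD × √(1 − r²). Power is from the noncentral t with 48.6 per group and a difference of 0.5. Brackets allow for rounding of the inputs (SD 0.75–0.85, change SD 0.95–1.05, r 0.545–0.555).

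| Reading | Week-4 SD | r | Residual SD | Power |
|---|---|---|---|---|
| (a) 0.8 is the baseline SD; all three numbers kept | 1.184 | 0.55 | 0.989 | 69% (64–76%) |
| (b) 0.8 is the week-4 SD; all three kept | 0.8 | 0.55 | 0.668 | 95% (93–97%) |
| (c) equal SDs, 0.8 dropped | 1.054 | 0.55 | 0.880 | 79% (75–83%) |
| (d) 0.8 at both visits, 0.55 dropped | 0.8 | 0.22 | 0.781 | 88% (84–91%) |
| (e) 0.8 at both visits, 1.0 a misprint for 0.76 | 0.8 | 0.55 | 0.668 | 95% (93–97%) |

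In (c) the common SD is 1.0/√(2 × 0.45) = 1.054. In (d) the correlation is 1 − 1.0²/(2 × 0.64) = 0.22.

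Under (a), power is 74% even with no loss. A 90% chance of detection needs a true difference of about 0.66 points, or 84 evaluable per group for 0.5 points.

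**The case against.** Several points can fairly be made for the plan.

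- *The three variance figures are not impossible together.* This stands: SDs of 0.8 and 1.18 satisfy them. A narrower spread at baseline is also plausible when entry requires a subscore of at least 3. But the plan states no SD of 1.18, and its sample size does not use one.
- *The figure of 108 can be reproduced, and on that basis the ANCOVA does better than 90%.* This also stands, as reading (e). It requires setting aside the listed change SD of 1.0.
- *The mislabelled line refers to 4 weeks, so striking out the word for change leaves a week-4 score and 95% power.* This is a legitimate reading. With all three numbers kept, however, it needs a baseline mean of 4.4 with SD 1.18. Under this trial's entry range of 3 to 5, the largest possible SD at mean 4.4 is √(0.6 × 1.4) = 0.92. The source trial's entry range is not given, so the reading may still describe those data. The 95% itself needs only a week-4 SD of 0.8 with r = 0.55.
- *The range under (d) includes 90%.* It does, but only by replacing the listed correlation of 0.55 with 0.22.
- *The practical consequence is limited.* Section 9.4.2 commits to an adjusted difference with a 95% confidence interval, which guards against over-reading a null result. It does not correct the power statement.

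**Conclusion.** The concern holds. One line is mislabelled, the single listed score SD does not give the listed change SD, and 108 comes from an unadjusted comparison rather than the ANCOVA that the plan names. Only readings (a) and (b) keep every listed number, and neither gives 90%: about 69% and about 95%. Across all readings the range is 69% to 95%.

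These figures assume a 0.5-point difference, two-sided 0.05, 10% loss in each group and the same residual SD in both groups. The inconsistency is certain from the text. Which power figure is right is not, and only the source placebo data can decide it. This should be fixed, but it does not invalidate the design.

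**What to change.** Using the source placebo data:

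1. Label 3.7 (0.8) as the baseline or the week-4 mean (SD), not as a change.
2. List a baseline SD, a week-4 SD, a correlation and a change SD that agree with one another.
3. Recompute power for the planned ANCOVA at 108 participants with 10% loss, and say how the 10% is applied (multiplying by 1.1 or dividing by 0.9).
4. Replace the 90% in sections 4.2 and 9.2 with the result. It would be about 70% for 0.5 points (90% for about 0.66 points) if a baseline SD of 0.8 and a change SD of 1.0 are confirmed with r = 0.55. It would be about 95% if 0.8 is the week-4 SD, or if 1.0 is a misprint for 0.76.

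Leave the sample size as it is. The cost is one look-up and new wording in two sections, with no extra participants and no change to endpoint, model or alpha. The stated power may go down or up.

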9.3 POPULATIONS FOR ANALYSES

Analysis datasets will include:

- a. Intention-to-Treat – all randomized participants
- b. Safety Analysis Dataset – participants who took at least one dose of treatment
- c. Other Datasets for Sensitivity analyses on a per-protocol basis (as needed: by etiology, sex, race, narcotic use, etc.)
 - i. Complete-Case Analysis Dataset – subset of participants with 4-week outcome data
 - ii. Adherence Analysis Dataset – subset of participants who took at least 80% of treatment

9.4 STATISTICAL ANALYSES

9.4.1 GENERAL APPROACH

The primary analysis is an intention-to-treat analysis of the change in the PAGI-SYM questionnaire postprandial fullness/early satiety subscore over 4-weeks of treatment. This subscore is calculated as the average of four items on the PAGI-SYM questionnaire: stomach fullness, inability to finish a normal-sized meal, feeling excessively full after meals, and loss of appetite. The subscore average and each item score ranges from 0 (none) to 5 (very severe) on an ordinal scale and is treated as a continuous measure. The statistical model for change in postprandial fullness/early satiety at 4-weeks will be an ANCOVA model with an indicator variable for treatment group adjusted for the baseline value of the postprandial fullness/early satiety subscore. If a participant has missing 4-week outcome data, then multiple imputation modeling for missing data will be used.

Secondary, sensitivity analyses on a per-protocol basis will also be carried out, excluding participants from both groups who do not have the 4-week outcome data, but conclusions about the primary objective will be based on the intention-to-treat analysis. In addition, sensitivity analysis may be done using the subset of participants with adherence (defined as taking their treatment at least 80% of the time).

9.4.2 ANALYSIS OF THE PRIMARY EFFICACY OUTCOME(S)

- Intention-to-Treat (ITT) Analysis Dataset

The primary outcome will be change in the PAGI-SYM questionnaire postprandial fullness/early satiety subscore from baseline to 4 weeks; this subscore is calculated by averaging the scores for 4 PAGI-SYM items: stomach fullness, inability to finish a normal-sized meal, feeling excessively full after meals, and loss of appetite. The subscore average and each item score ranges from 0 (none) to 5 (very severe) on an ordinal scale and is treated as a continuous measure. The treatment effect will be estimated using an intention-to-treat (ITT) analysis of covariance (ANCOVA) model, regressing the change from baseline in postprandial fullness/early satiety subscore at 4-weeks on an indicator variable for treatment group and the baseline value of the outcome. The treatment group difference in adjusted mean change will be presented, along with a two-sided 95% confidence interval, and a P-value.

The confidence limits and P-value will come from the Intention-to-Treat multiple imputation ANCOVA model using all randomized participants, corrected for missing data, as described in [Section 9.2](#) above.

Descriptive analyses will address the assumption of normality of the outcomes using distributional tests (Shapiro-Wilks) and plots (lowess smoothed histograms, boxplots). Tests of normality of the residuals post-ANCOVA regression will be done. If the normality assumptions are not met, then sensitivity analyses using bootstrapped ANCOVA regression will be used to assess validity of the confidence limits and P-values.

Secondary, sensitivity analyses of the primary outcome will use the ITT Dataset and include:

- Complete case ANCOVA, excluding participants with missing data
- The same analysis as above comparing subsets of participants with high vs. not high adherence
- Repeat the Intention-to-Treat analysis adjusting for potential confounders not balanced by the randomization, such as use of narcotics, gastroparesis etiology, percent gastric retention, sex, and age.
- Other secondary, sensitivity analysis conducted will be to model each of the four individual symptom scores of the PAGI-SYM questionnaire postprandial fullness/early satiety subscore using the same methods as above.
- Graphs plotting the time course of mean change scores of the outcome and two-sided 95% confidence intervals by treatment group across visit (screening, 2, 4, 6 weeks) will be done. The significance of the overall treatment effect of change over time will be computed from generalized estimating equations (GEE) linear regression, modeling change as a function of treatment group, visit code indicator, baseline value of the outcome, and a treatment group by visit code interaction term.
- Using the PRO GCSI-DD, the two items, “not able to finish a normal-sized meal” and “feeling excessively full after meals” will be averaged to measure postprandial fullness/early satiety. The same method as above will be used; however, the baseline value is the average of the 7-day screening period daily-diary responses, and the 4-week measure is the average of the last 7-days of treatment. The change in each outcome is computed as the baseline average value subtracted from the 4-week average measure. A sensitivity analysis using a repeated measures method to account for within participant correlation will also be used.

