4 STUDY DESIGN

4.1 OVERALL DESIGN

- The primary hypothesis of the trial is that buspirone treatment improves early satiety and postprandial fullness as measured by the PAGI-SYM questionnaire postprandial fullness/early satiety subscore; we will test this hypothesis by comparing the mean change from baseline in this subscore over the 4 weeks of treatment in the group treated with buspirone to the mean change from baseline in this subscore in the group treated with placebo (ANCOVA test for mean between-group differences in differences using baseline value as the covariate)
- Phase 2
- A multi-center, randomized, double-masked, placebo-controlled, parallel treatment groups phase 2 trial with primary outcome defined as symptomatic improvement in early satiety and postprandial fullness. The primary outcome is the change in the postprandial fullness/early satiety subscore from baseline to 4 weeks; this subscore is calculated by averaging the scores for 4 PAGI-SYM questionnaire items: stomach fullness, inability to finish a normal-sized meal, feeling excessively full after meals, and loss of appetite.
- Methods to decrease bias will include placebo control, double masking and randomization.
- Two study arms
- Multisite
- Study intervention is buspirone 10 mg capsule three times daily, 30 minutes before each meal, for 4 weeks or matching placebo.
- The randomization design will be stratified by clinical center with participants' assignments into one of two groups (buspirone or placebo) in permuted blocks of random length within each clinic.

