6.3 MEASURES TO MINIMIZE BIAS: RANDOMIZATION AND BLINDING

Randomization: The randomization scheme will assign participants in randomly permuted blocks of assignments stratified by clinical center. This scheme will ensure that the two groups will be of nearly equal size and will be balanced by calendar time of enrollment to ensure equal numbers of participants by time of enrollment (to minimize secular effects) and by clinic (to minimize clinic effects).

The randomization plan will be prepared and administered centrally, using a secure web application, by the SDRC. An assignment will be issued only if the trial database shows that the participant is eligible, has signed the consent statement, and has had all required baseline data keyed to the data system.

Treatment assignments are double-masked throughout the study until all data collection for the BESST trial has been completed, i.e., after completion of the 2-week post-trial follow-up visit for all participants. Every effort will be made to maintain the masking throughout the study except in emergency situations. The randomization code masking the bottle contents will not be provided by the SDRC without the knowledge of the clinical center's principal investigator.

Unmasking of study medication will occur under the following conditions:

- **Severe allergic reaction (Stevens-Johnson Syndrome):** Study medication is stopped indefinitely. The participant, primary care provider (PCP), and the investigator will be unmasked.
- **Pregnancy during the study:** Study medication will be stopped indefinitely, and the coded medication will be unmasked. The participant, PCP, and investigator will be notified of the assigned treatment and the associated risks of teratogenicity.

In unforeseen situations where the clinical center principal investigator considers unmasking is in the best interest of the participant's health and well-being, unmasking may be done after notifying the Executive Committee. The Data and Safety Monitoring Board will review all instances of unmasking that have occurred.

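### Randomisation is stratified by clinical center, but the primary and continuous secondary ANCOVAs omit clinic; if clinic is prognostic after baseline, the confidence interval is too wide and the test conservative.

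*Combined protocol and SAP*

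**What the plan says.** Treatment is assigned in permuted blocks within each of six clinics (sections 4.1 and 6.3). Section 6.3 gives the purpose as balance over enrolment time "and by clinic (to minimize clinic effects").

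The primary model is described four times, never with clinic:

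- Section 4.1: "ANCOVA test for mean between-group differences in differences using baseline value as the covariate".
- Section 9.2: "ANCOVA of the change in the primary outcome score controlling for baseline value of the primary outcome score".
- Section 9.4.1: "ANCOVA model with an indicator variable for treatment group adjusted for the baseline value of the postprandial fullness/early satiety subscore".
- Section 9.4.2: change in the "subscore at 4-weeks on an indicator variable for treatment group and the baseline value of the outcome".

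Section 9.4.3 gives the continuous secondary outcomes the same two terms.

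For missing primary outcomes, section 9.2 specifies "Multiple imputation of the ANCOVA model using the chained equations method with 50 imputations" and lists no separate predictors. For secondary outcomes that are imputed, section 9.4.3 names treatment and the baseline value as predictors.

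Clinic appears in the analysis plan only in section 9.4.7, as a post-hoc subgroup factor with an interaction test. The covariate-adjusted sensitivity analysis in 9.4.2 is aimed at factors that randomisation left uneven. Its list is open-ended but does not name clinic. No reason is given for leaving clinic out.

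**The concern.** Stratified blocking makes the arms nearly equal within each clinic, so differences between clinics largely cancel out of the treatment comparison. The benefit reaches the reported result only if the analysis also removes those differences from the residual variance. When clinic is left out, the model computes its standard error as though clinic differences still added noise to the comparison.

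What is at stake is calibration and efficiency. The primary conclusion rests on one confidence interval and one P-value. If clinics differ, that interval covers more than 95% of the time and the test rejects less than 5% of the time under the null, so part of what the stratification bought is not used.

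**Working it through.** **Inputs from the documents.** Section 9.2 gives two-sided 0.05, 90% power, equal groups, a difference of 0.5 points (0.62 SD), SD 0.8, SD of change 1.0, baseline to week-4 correlation 0.55 and 10% outcome loss. Section 5.5.1 gives six centers averaging 18 participants.

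**Assumptions.** The share *s* of residual variance (after baseline) due to clinic is 0, 5, 10 or 20%. Clinics are of equal size, with blocks of 2 or 4.

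**The plan's own figure.** SD of change = 0.8 × √(2 × (1 − 0.55)) = 0.759. Per group, n = 2 × (1.960 + 1.282)² × 0.759² / 0.5² = 48.4, so 49. Section 9.2 then says "Sample size increased by 10% to allow for 10% loss in primary outcome measure": 49 × 1.10 = 53.9, so 54 per group and 108 in total. The stated size reproduces without any clinic term.

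**Residual SDs that section 9.2 allows.**

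- 0.5 / 0.62 = 0.806, about 0.8.
- 0.8 × √(1 − 0.55²) = 0.668.
- From the change SD of 1.0: s₄² − 2 × 0.55 × 0.8 × s₄ + 0.8² = 1 gives a week-4 SD s₄ = 1.184, and 1.184 × √(1 − 0.55²) = 0.99.

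**Expected effect on the standard error.** With balanced clinics the true variance of the estimate is proportional to 1 − s. Six clinic effects drawn at random realise on average 5/6 of their nominal variance, so the model without clinic works with about 1 − s + 5s/6. The SE ratio (without / with clinic) is √((1 − s + 5s/6)/(1 − s)) = 1.022, 1.045 and 1.099 at 5, 10 and 20%.

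**Simulation with complete outcomes** (null, residual SD 1.0, 20,000 runs per cell). The ratios were 0.999, 1.021, 1.045 and 1.099 at 0, 5, 10 and 20%, as expected. Without clinic, the mean reported SE against the actual SD of the estimate was 0.1913 against 0.1836 at 10%, and 0.1895 against 0.1737 at 20%.

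**Simulation with 10% of outcomes missing completely at random** (complete cases, 20,000 runs per cell). Power is for 0.5 points, without / with clinic, in %.

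| Clinic share | SE ratio | Type I error without clinic | Power, SD 0.668 | Power, SD 0.8 | Power, SD 0.99 |
|---|---|---|---|---|---|
| 0% | 0.997 | 4.9% | 95.1 / 95.0 | 85.9 / 85.8 | 68.8 / 68.5 |
| 5% | 1.018 | 4.7% | 95.7 / 95.9 | 86.4 / 87.1 | 69.1 / 70.2 |
| 10% | 1.042 | 4.2% | 95.9 / 96.6 | 87.2 / 88.9 | 69.9 / 72.8 |
| 20% | 1.096 | 3.3% | 96.9 / 98.2 | 88.6 / 91.9 | 72.2 / 78.2 |

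With clinic in the model, type I error was 4.8 to 5.0% (Monte Carlo SE 0.15 points). The level of power depends on which SD is right; the point here is the difference within each pair.

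**With multiple imputation as planned** (50 imputations, 10,000 runs). Type I error of the planned model was 4.7, 4.7, 4.4 and 3.2%. Power at SD 0.8, for the planned model / clinic in both analysis and imputation, was 85.0/84.7, 86.1/87.0, 87.4/88.8 and 88.1/91.8%. With clinic in the analysis but not in the imputation, the SE was 0.3, 1.0 and 2.6% larger than with matching models at 5, 10 and 20%.

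**Separate run with clinic effects of fixed size** (SD 0.668, blocks of 2, 4 or 6, no missing data). Interval width ratios were 1.025, 1.053 and 1.119, and type I error was 4.5, 3.8 and 2.8%. The table is therefore the more modest version.

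**The case against.** The best case against acting is that nothing here is invalid. The planned test respects its 5% level, the estimate is unbiased, and 108 reproduces without clinic. Whether anything is lost depends on a variance that the documents do not give. A patient-completed questionnaire, common entry thresholds and shared standard-of-care guidance all suggest small clinic differences. SD 0.8 is the scale used to express the MCID. With correlation 0.55 the baseline-adjusted SD is 0.668, where the gain is only 0.2, 0.7 and 1.3 points.

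Equal clinics and short blocks are also favourable assumptions. With clinics of 40, 28, 18, 12, 6 and 4 and blocks of 4, 6 or 8, the SE excess falls to about 1.3% at a 5% share and 3.4% at 10%, with type I error about 5.0 and 4.3% (Monte Carlo SE about 0.3 points). A clinic-adjusted sensitivity analysis might then be enough.

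Much of this stands: the effect is small at shares of 5% or less, and its size is unknown. It does not remove the case for change, because the costs are lopsided. With no clinic effect, adding clinic costs 0.1 to 0.3 points in the table; with a real one it restores nominal coverage and gains power. A sensitivity analysis would leave the primary interval miscalibrated. Nor do the clinic subgroups in 9.4.7 help, since they test whether the effect differs by clinic and give no clinic-adjusted overall effect.

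**Conclusion.** The concern holds. The randomisation stratifier is missing from every statement of the primary ANCOVA and from the continuous secondary ANCOVAs, and no other section supplies a clinic-adjusted treatment effect. The consequence is conditional: if clinic explains outcome after baseline, intervals are wider than they need to be and the test runs below 5%.

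The omission and the direction of its effect are certain. The size rests on the assumed clinic share, near-equal clinics and outcomes missing completely at random. From the table, the power difference at residual SD 0.8 is 0.7, 1.7 and 3.3 points at shares of 5, 10 and 20%; at SD 0.99 it reaches 6.0 points at 20%. This is a change worth making, but the trial's validity does not depend on it.

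**What to change.** Before unmasking, prespecify clinic as a fixed effect (five indicator terms) in the primary ANCOVA and the continuous secondary ANCOVAs, and bring sections 4.1, 9.2, 9.4.1, 9.4.2 and 9.4.3 into line. Add clinic to the imputation predictors named in 9.4.3. In 9.2, state the predictors for the primary outcome, including clinic. Keep the baseline-only ANCOVA as a sensitivity analysis. Because center sizes may be unequal, also state in advance how a very small clinic will be handled.

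Leave the logistic model for GCSI improvement as it is, since clinic terms would change the odds ratio being estimated. The GEE time-course model is outside this point.

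The cost is a protocol amendment, which under the Statement of Compliance goes to NIDDK, then the IRB, and is sent to the FDA. It uses five residual degrees of freedom: with 10% loss about 97 participants remain, so 97 − 3 = 94 becomes 97 − 8 = 89. The sample size stays at 108 and no new data are needed, because clinic is known for everyone.
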